8.2 Procedures

Our study will follow the design outlined above (section 5.1).

There is no informed consent needed for the use of this data. There will be no participant recruitment or compensation. Potential risks and benefits of the study are reported elsewhere (section 11.6).

Two CRCs will be hired to analyze de-identified patient data. CRCs will access the data via a password-protected portal, using a UPHS desktop and/or laptop. De-identified patient chart data will be included for analysis based on having a tumor type of interest. They will then review patient charts and record clinical elements of interest in the Mendel abstraction tool, which will be secured in a HIPAA-compliant external enclave. Summary-level data will be exported into datasheets for analysis. These datasheets will only be used and analyzed on UPHS equipment, or shared via HIPAA-compliant means.

Data will be analyzed using statistical software including Excel, R code, and STATA. For details of the analysis plan, see section 9.

Data elements that will be abstracted across all arms of the study include the following (the below list may change slightly pending further discussion among the research team):

Cancer Type and Staging

- Cancer Type
- Stage - Tumor
- Stage - Node
- Stage - Mets

Performance

- ECOG Performance Status

Prior Systemic Treatment

- Any Prior Platinum Therapy (e.g., Cisplatin, Carboplatin, Oxaliplatin)
- Any Other Prior Chemotherapy (e.g., 5-fluorouracil, Leucovorin, Capecitabine, Irinotecan, Pemetrexed, Paclitaxel, Docetaxel, Gemcitabine)
- Any Prior Immunotherapy (e.g., Atezolizumab, Nivolumab, Pembrolizumab)

Biomarkers for CRC

- KRAS
- MSI-H
- MSS
- BRAF
- HER2
- NTRK
- DPYD

Biomarkers for NSCLC

- EGFR
- ALK
- ROS1
- KRAS
- BRAF
- NTRK
- cMET
- RET
- PDL1

Others

- Outcomes (remission, residual disease, recurrence, loco-regional recurrence, distant recurrence)
- Responses (complete response, stable disease, partial response, mixed response, disease progression)

9. Analysis plan

The primary study will be powered on a retrospective paired, non-inferiority design to evaluate abstraction accuracy of elements commonly used to help screen patients for clinical trials. The two arms are (1) human reviewers versus (2) human reviewers utilizing predictions from Mendel AI. The primary outcome, the percentage of gold standard items correctly abstracted, will be measured for each chart. Noninferiority can be established by comparing the difference in the

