mean proportion correct between the human-augmented and Human-alone arms with a predefined non-inferiority margin, Δ .

The one-sided hypotheses to test noninferiority of average chart-level accuracy of a Human+AI abstraction approach, compared with a Human-alone approach are outlined below:

$$H_0: \mu_{h-ai} - \mu_h \leq -\Delta \text{ (Null hypothesis)}$$

$$H_a: \mu_{h-ai} - \mu_h > -\Delta \text{ (Alternative hypothesis)}$$

Test statistic:

$$T_n = \frac{(\mu_{h-ai} - \mu_h) + \Delta}{\sqrt{\frac{Var(D)}{n}}}$$

Sample size equation for a noninferiority, paired study design:

$$n = \frac{(z_{1-\beta} + z_{1-\alpha})^2 \sigma^2}{((\mu_{h-ai} - \mu_h) + \Delta)^2} = \frac{(z_{1-\beta} + z_{1-\alpha})^2 \sigma^2}{(D + \Delta)^2}$$

As a secondary analysis, we will test the superiority of the Human+AI arm for achieving greater average chart-level accuracy, compared with the Human-alone arm. Our hypotheses are:

$$H_0: \mu_{h-ai} \leq \mu_h \text{ (Null hypothesis)}$$

$$H_a: \mu_{h-ai} > \mu_h \text{ (Alternative hypothesis)}$$

Sample size equation for a superiority, paired study design:

$$n = \frac{(z_{1-\beta} + z_{1-\alpha})^2 Var(D)}{(\mu_{h-ai} - \mu_h)^2}$$

Parameter	Description
μ_{h-ai}	Mean proportion of criteria correctly abstracted by AI-augmented human reviewers
μ_h	Mean proportion of criteria correctly abstracted by Human-alone reviewers
$D = \mu_{h-ai} - \mu_h$	Mean difference in chart-level accuracy between arms
Δ	Non-inferiority margin, set as 0.05 for conservative sample size estimates.
$z_{1-\beta}$	Critical value at $1-\beta$, where $1-\beta$ represents the desired power and β represents Type II error

$Z_{1-\alpha}$	Critical value at $1-\alpha$, where α = Type I error
σ^2	$n^* \text{Var}(D)$, where n is the sample size and $\text{Var}(D)$ is the variance of the mean difference in chart-level accuracy

*Note: μ_{h-ai} , μ_h , $\Delta > 0$.

From our initial calculations, 400 individual patients will achieve an estimated statistical power greater than 90% for this non-inferiority study with a Type I error of 5%. This was determined from simulations for different realistic parameter scenarios for TNR, event rate, and concordance assumptions showing that the needed sample size rarely exceeded 400.

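### Section 9 uses Var(D) in two incompatible senses, so the written primary test statistic does not hold the stated 5% Type I error if the parameter table is followed literally

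*Combined protocol and SAP*

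**What the plan says.** Section 9 describes a "retrospective paired, non-inferiority design" with chart-level accuracy as the outcome, a margin Δ of 0.05 and one-sided hypotheses. Five elements of that section use or define the variance:

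- **Row D of the parameter table:** "Mean difference in chart-level accuracy between arms". D is an average, not a difference on one chart.
- **Row σ² of the table:** σ² is n times Var(D), and Var(D) "is the variance of the mean difference in chart-level accuracy".
- **Non-inferiority sample size equation:** n = (sum of the two z values)² × σ² / (D + Δ)².
- **Test statistic:** T_n = (mean difference + Δ) / √(Var(D)/n).
- **Superiority sample size equation:** n = (sum of the two z values)² × Var(D) / (mean difference)².

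The critical value z(1−α) is defined with the words "where α = Type I error". The error rate is stated "for this non-inferiority study with a Type I error of 5" per cent, with power above 90% for 400 patients. The plan credits the 400 to simulations. It gives no numerical value for the standard deviation (SD) of the paired differences.

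**The concern.** The same symbol is the variance of an average in the table and has to be the variance of a single chart's difference in two of the three formulas. The table and the non-inferiority equation agree with each other. T_n and the superiority equation agree with each other. The two pairs do not agree.

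This matters because T_n is the only formula given for the primary test. The paired t-test named later in Section 9 is for superiority and for criterion-level accuracy, not for the primary comparison. An analyst who programs T_n with the plan's own definition of Var(D) divides by n twice. The standard error is then far too small, and non-inferiority could be declared when the standard paired test would not declare it.

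**Working it through.** **Inputs.** From Section 9: one-sided α = 0.05, power 90%, Δ = 0.05, n = 400. Hence z(0.95) = 1.645, z(0.90) = 1.282 and (sum)² = 8.564. Assumed: per-chart SD of the paired differences, S, from 0.10 to 0.34; differences independent across charts; estimated means in the numerator of T_n; non-inferiority concluded if T_n > 1.645.

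**The plan's own figure.** The 400 cannot be reproduced, because the documents give neither S nor the simulation settings. With one consistent per-chart variance and D = 0, n = 8.564 × S² / 0.0025. This gives 138 at S = 0.20 and 396 at S = 0.34. The largest S that gives 90% power with 400 charts is √(400 × 0.0025 / 8.564) = 0.342.

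**A check that needs no choice of reading.** Setting Δ = 0 in the non-inferiority equation should return the superiority equation. With σ² = n × Var(D), the first becomes 8.564 × n × Var(D)/D² and the second is 8.564 × Var(D)/D². They differ by a factor of n.

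**Table meaning everywhere, Var(D) = S²/n.**
- The non-inferiority equation is correct, since σ² = S².
- T_n divides by √(S²/n²) = S/n instead of S/√n. It is too large by √400 = 20. At the margin, P(T_n > 1.645) = 1 − Φ(1.645/20) = 0.467, whatever S is. A simulation of 20,000 trials at S = 0.20 gave 0.472, against 0.051 with the per-chart variance.
- The superiority equation has n on both sides and solves to the square root of the right answer. At S = 0.20 and D = 0.02 (both assumed), the right answer is 8.564 × 0.04/0.0004, or 857 after rounding up. The equation gives 30.

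**Per-chart meaning everywhere, Var(D) = S².**
- T_n and the superiority equation are correct.
- The non-inferiority equation fails: σ² = n × S² makes n cancel, so it yields no sample size. Putting n = 400 into σ² at S = 0.20 returns 8.564 × 400 × 0.04/0.0025, about 54,809 with unrounded z values, instead of 138.

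**Where the decision would change.** The literal T_n and the standard test disagree only if the observed difference lies between −0.05 + 1.645 × S/400 and −0.05 + 1.645 × S/20.

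| S (assumed) | Band of observed difference | Chance of falling in it if the true difference is 0 |
|---|---|---|
| 0.10 | −0.0496 to −0.0418 | under 0.01% |
| 0.20 | −0.0492 to −0.0336 | 0.04% |
| 0.34 | −0.0486 to −0.0220 | 9.5% |

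If the true difference is exactly at the margin, the chance is 0.467 − 0.05 = 0.417 for every S.

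**The case against.** The strongest reply is that this is notation only. Section 8.2 says the analysis will use standard software, and a paired routine computes the right standard error from the chart-level differences. The 47% belongs to someone who codes T_n by hand from the table. No sample size is reported from the superiority equation. The 9.5% rests on S = 0.34, which is back-solved as about the largest value compatible with 90% power and is not an estimate. As an illustration, 12 criteria per chart with independent errors and 50% accuracy in both arms would give √(2 × 0.25/12), about 0.20, although clustered errors or fewer scorable items could raise it. All of this stands. It limits the practical weight but does not make the formulas consistent.

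The PDF reading may have lost a bar over D. That cannot be excluded from the text, but row D defines the symbol in words as an average, and no per-chart difference is defined anywhere.

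A reader might infer that the σ² row is the mistake. The documents do not support that. The row is algebraically sound (n times the variance of an average is the per-chart variance), it fits row D, and it makes the non-inferiority equation correct. The paired design, the 5% error rate and the later paired t-test show what the test must compute. They do not show which line departs from it.

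**Conclusion.** Var(D) carries two incompatible meanings in Section 9, and neither makes all three formulas work. On the table's own definition with 400 charts, T_n is inflated 20-fold and its Type I error at the margin is about 47% against the stated 5%. That result does not depend on S, but it assumes comparison with 1.645 and independent charts. The width of the affected band does depend on S, which the documents do not give.

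Two stronger conclusions are tempting and unsupported. One is that the trial will run at a 47% error rate: this is a property of the written formula, not of a standard paired t-test. The other is that 400 is wrong: the plan attributes it to simulations, and nothing shows that the conflict entered them. The point is a minor correction to the specification of the primary test.

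**What to change.** Choose one convention and apply it throughout Section 9. Either of these works, and both give the same numbers:

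1. **Smallest edit.** Keep the table and the non-inferiority equation. Write T_n over √Var(D), which equals √(σ²/n), and replace Var(D) by σ² in the superiority equation.
2. **Per-chart notation.** Define d_i as Human+AI accuracy minus Human-alone accuracy on chart i, with variance S_d² across charts. Set σ² = S_d², removing the factor n and the row's description of Var(D) together. Use S_d²/n in T_n and S_d² in both sample size equations.

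Under the second option, rewording the description while leaving the factor n in place would break the non-inferiority equation. The cost is a few notation edits, with no change to data, design or sample size.

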The objective of this study is to assess and compare the accuracy and efficiency of three different approaches to abstracting clinical data used to identify oncology patients who meet the inclusion criteria for participation in clinical trials. The three approaches under evaluation include: (1) an autonomous AI algorithm (Mendel AI; developed by artificial intelligence startup company Mendel) which analyzes patient medical records to extract relevant clinical facts (“AI-alone”); (2) a human researcher who manually reviews patient charts as per the current norm/practice (“Human-alone”); and (3) a human researcher utilizing AI augmentation (“Human+AI”), where Mendel AI serves as a supportive tool in the decision-making process by providing the researcher a list of elements abstracted by the AI algorithm and a rank-order list of patients most likely to meet inclusion criteria for a trial.

The study primarily aims to compare (1) the chart-level accuracy of the Human+AI collaboration relative to Human-alone given the relevance of this comparison for real-world clinical workflows, defined by the percentage of pre-identified chart elements classified correctly compared against a predetermined “gold standard”; and (2) the efficiency of the Human+AI vs. Human-alone arms, defined by the time per chart review in minutes, measured for each chart.

Our hypotheses are (1) the Human+AI arm will be non-inferior in accuracy when compared to the Human-alone arm, in relation to a predetermined “gold standard”, and (2) that a Human+AI arm will be superior in speed of abstraction when compared to Human-alone screening.

The identification of eligible patients for clinical trials is a critical component of clinical research, as it directly impacts patient recruitment, study enrollment, and the generalizability of research findings. Currently, the process of identifying eligible patients often relies on manual chart review by clinical research staff, which can be time-consuming, labor-intensive, and prone

to human error. Consequently, eligible patients may be overlooked, and opportunities for trial participation may be missed. The integration of AI technology into the patient identification process has the potential to enhance the accuracy and efficiency of this critical task, leading to improved clinical trial recruitment and outcomes.

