5.1 Design

In this experimental study, we will employ a three-arm design including (1) AI-alone, (2) Human-alone, (3) Human+AI to assess the accuracy of abstracting clinical elements from the patient chart. The accuracy of the abstraction will be compared against a pre-made “gold standard”. As detailed elsewhere, the study is powered for a direct comparison of the human alone vs human + AI arms as a non-inferiority analysis. For Arm 1, an autonomous AI algorithm (Mendel AI) will analyze patient medical records to extract relevant clinical elements (“AI-alone”). For Arm 2, a human researcher will manually review patient charts as per the current norm/practice (“Human-alone”). For Arm 3, a human researcher will utilize Mendel AI augmentation such that Mendel AI serves as a supportive tool in the decision-making process by providing the researcher a list of elements abstracted by the AI algorithm and a rank-order list of patients most likely to meet inclusion criteria for a trial (“Human+AI”). **For this study, we will**

only be using information from deidentified patient charts in Mendel's database. No Penn data will be utilized in this study.

We will employ 2 clinical research coordinators (CRCs) who will review and abstract specific clinical elements while reviewing the patient's electronic health record (EHR) which will include both "structured" (machine-readable) and "unstructured" (traditionally non-machine-readable; Mendel AI is uniquely capable of processing) data. To ensure no inter-rater differences in accuracy the CRCs will be assessed on a practice set of three charts and must meet an 80% threshold of agreement on review elements as well as concordance in chart-level accuracy as measured by Cohen's Kappa (threshold 0.6).

The components of the EHR that may be reviewed to abstract the data elements of interest may include:

- Physician Progress Notes
- Radiology Reports
- Pathology Reports
- Laboratory Reports
- Genetic/molecular sequencing and other genetic testing results
- Discharge Summaries
- Infusion Therapy reports

To help assess accuracy, the "Gold Standard" (to which all study arms will be compared) will be a manually annotated version based on review of at least 2 human abstractors (plus a tie-breaker if there is a discrepancy). This process will be led by the Mendel team, with independent oversight by the Penn research team to ensure consistency.

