First, the Mendel AI algorithm will review all patient charts, producing a machine-annotated version of each chart with AI-abstracted elements (AI-alone). Next, each CRC will review all patient charts. Each CRC will review half of their charts manually (Human-alone) and half of their charts using the machine-annotation and rank-order list (Human+AI). The order of review will be randomized such that manual reviews and AI-assisted reviews will be mixed, and such that each CRC will review half of the charts manually and half of the charts with AI assistance.

Secondary aim metrics (Efficiency) will be assessed by tracking the volume of completed prescreens per unit of time.

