The goals of the secondary analyses are to compare the efficiency of screening among the three study arms. We will analyze efficiency, defined by comparing the average number of minutes per chart review, measured for each chart. A nonparametric, paired Wilcoxon Rank Sum test with continuity correction will compare overall median efficiency of chart abstraction between arms.

The following are post-hoc analyses to be conducted after the pre-specified main analyses. Superiority of chart-level accuracy for the Human+AI arm relative to Human-alone will be tested using a one-sided paired t-test with an unspecified inferiority margin. A sensitivity analysis will repeat the primary chart-level accuracy outcome analysis with a less strict definition of an accurate match to the gold standard set. To assess whether there is a difference in accuracy among the 12 trial eligibility criteria, criterion-level accuracy will be compared assessed between arms. To assess criterion-level accuracy, a two-sided, paired t-test will be conducted with Bonferroni correction for multiple hypotheses (i.e., $\alpha = 0.05 / n$, where $n=12$ was the number of criteria studied). For any criterion with a statistically significant difference in mean criterion-level accuracy, superiority of the Human+AI arm for criterion-level abstraction will be then assessed with an additional one-sided hypothesis with an unspecified superiority margin. Lastly, we repeat both the chart-level accuracy analysis and efficiency analyses while stratifying by chart characteristics that include chart complexity, length, order, and cancer type.

Descriptive statistics, including means, medians, proportions, and ranges, will be used to summarize each analyses. All statistical analyses will be conducted using appropriate statistical software, and will rely on a predetermined significance level (e.g., $\alpha = 0.05$). Effect sizes and confidence intervals will be reported where applicable to provide further context to the findings.

10. Investigators

[name], PhD (Principal Investigator) is [name] and [name] University Professor in Health Policy and Medical Ethics and Co-Director of the Healthcare Transformation Institute.

[name], MPP (Sub-Investigator) is Assistant Professor of Health Policy and Medicine and Innovation Faculty at the Penn Center for Cancer Care Innovation (PC3I).

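### The efficiency test is misnamed and, read as signed-rank, treats the coordinators' speed gap as noise, so the test is conservative and its interval too wide, though the estimate stays sound

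*Combined protocol and SAP*

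**What the plan says.** Section 9 defines efficiency as minutes per chart review and gives the test in one sentence: "A nonparametric, paired Wilcoxon Rank Sum test with continuity correction will compare overall median efficiency of chart abstraction between arms". The same section describes the main comparison as paired: "The primary study will be powered on a retrospective paired, non-inferiority design".

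Section 5.1 employs two coordinators and sets the allocation: "Next, each CRC will review all patient charts", and then "Each CRC will review half of their charts manually (Human-alone) and half of their charts using the machine-annotation and rank-order list (Human+AI"). It does not say outright that one coordinator's manual half is the other's AI-assisted half.

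The coordinators are calibrated beforehand (Section 5.1): "To ensure no inter-rater differences in accuracy the CRCs will be assessed on a practice set of three charts". The thresholds there concern agreement and accuracy; none concerns speed. Among the post-hoc analyses, Section 9 says "we repeat both the chart-level accuracy analysis and efficiency analyses while stratifying by chart characteristics that include chart complexity, length, order, and cancer type". Coordinator is not in that list.

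Faster review is the second hypothesis in Section 2: "that a Human+AI arm will be superior in speed of abstraction when compared to Human-alone screening". Section 3.2 lists efficiency as the secondary aim.

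**The concern.** There are two faults, one of name and one of fit.

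The name joins a paired design to a test for independent samples. A programmer who follows it literally would discard the pairing by chart. Since the plan speaks of pairing twice, a slip for signed-rank is much the likelier explanation.

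The fit matters more. With two coordinators and one review each per chart, every chart that contributes one time per arm contrasts one person with the other. The difference holds the AI effect plus or minus the coordinators' difference in speed. Nothing in the calibration, the test or the listed strata takes that difference out. At stake are the power of the speed comparison for a small saving and the width of the interval around the time saved, which is the figure a reader would use.

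**Working it through.** **The plan's own figure.** Section 9 states that "400 individual patients will achieve an estimated statistical power greater than 90% for this non-inferiority study". Its formula, with margin 0.05, true difference 0 and one-sided 5%, allows an SD of the within-chart accuracy difference up to 0.05 × √400 / (1.282 + 1.645) = 0.342. The plan gives no SD, so the 400 is plausible but cannot be reproduced. It concerns accuracy; there is no power figure for efficiency. Only n = 400 is carried forward.

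**Assumed inputs, none of them in the documents.** Minutes are log-normal with log-SD √(0.6² + 0.35²) = 0.695. Within-chart correlation ρ is 0.75, 0.5 or 0.3. The speed gap g between coordinators is 0.4 on the log scale (exp 0.4 ≈ 1.5 times) or 0.2 (about 1.2 times). The log effect e is −0.08 (about 8% saving) or −0.163 (about 15%).

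**What a difference contains.** Where coordinator 1 had AI, d = e + g + noise. Where coordinator 2 had AI, d = e − g + noise. Let a and b be the numbers of such charts and c the number read with AI by both. Each coordinator uses AI on half the charts, so a + c = b + c, and a = b. The gap averages to zero. In simulation at g = 0.4, ρ = 0.75, the mean estimate was −0.164 for a true −0.163.

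**Actual against reported precision.** The noise variance is v = 2(1 − ρ) × 0.695². With a fixed 200:200 split the estimate has standard error √(v/400), but a test that ignores coordinator sees √((v + g²)/400). At g = 0.4:

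| ρ | v | actual SE | SE as signed-rank sees it | ratio | simulated interval widths |
|---|---|---|---|---|---|
| 0.75 | 0.241 | 0.0246 | 0.0317 | 1.29 | 0.1304 vs 0.0987 (32% wider) |
| 0.5 | 0.483 | 0.0347 | 0.0401 | 1.15 | 0.1629 vs 0.1399 (16%) |
| 0.3 | 0.676 | 0.0411 | 0.0457 | 1.11 | 0.1849 vs 0.1655 (12%) |

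The widths are for Hodges-Lehmann intervals on the log ratio, unadjusted against adjusted, at a 15% saving. The simulated SD of the estimate at ρ = 0.75 was 0.0246 with the gap and 0.0238 without: it hardly moves, while the reported SE rises to 0.0317.

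**Error rate and power** (4,000 runs per setting, two-sided 5%, g = 0.4). The adjusted test takes log(coordinator 1 minutes / coordinator 2 minutes) per chart and compares it between the two allocation groups by a Wilcoxon test. The groups centre on g + e and g − e, so g drops out and half the shift is e.

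| | ρ = 0.75 | 0.5 | 0.3 |
|---|---|---|---|
| Type I error, signed-rank on logs | 1.0% | 2.2% | 3.2% |
| Type I error, adjusted | 5.0% | 5.1% | 5.3% |
| Power, 8% saving, signed-rank on logs | 72% | 50% | 39% |
| Power, 8% saving, signed-rank on raw minutes | 63% | 46% | 36% |
| Power, 8% saving, adjusted | 89% | 63% | 48% |
| Power, 15% saving, signed-rank on logs | 100% | 98.9% | 95.2% |
| Power, 15% saving, adjusted | 100% | 99.6% | 97.0% |

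A one-sided 5% test at the 8% saving gives about 85% to 52% unadjusted against 94% to 59% adjusted, from ρ = 0.75 to 0.3. At g = 0.2, ρ = 0.75, two-sided, it is 86% against 89%, with the interval 8% wider (0.1069 vs 0.0987). With no gap both tests have 89%.

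**Literal rank-sum, no gap.** Power at the 8% saving is 23% against 89% for signed-rank at ρ = 0.75, and 33% against 48% at ρ = 0.3.

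**Strata.** In a stratum of 100 charts the split between allocations is not fixed: its 95% range is 42:58 to 58:42. At g = 0.4 that shifts the unadjusted log ratio by up to 0.4 × 0.16 = 0.064, about 6-7%. This is the edge of the range; the SD of the shift is about 3.5%. Simulated two-sided Type I error in such strata was 3.9% to 4.5%, so the test stays valid.

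**The case against.** The strongest reply is that little is lost. A conservative test cannot produce a false claim, the data behind the point estimate are fully used, and at a 15% saving power is above 95% without adjustment. The marked losses need a 1.5-fold gap together with a small saving. The speed hypothesis is directional and the sidedness of the test is not stated, so the one-sided figures, where the loss is smaller, may be the relevant ones. All of this stands and limits the weight of the point. It does not answer the wrong test name, or the overwide interval, which remains whatever the saving.

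Two stronger readings are tempting. A reader might infer that the gap biases the comparison in favour of one arm. The half-and-half allocation rules that out on the log scale, provided the balance holds in the analysed charts. On raw minutes a multiplicative gap moves the median difference only modestly: with an assumed 30-minute median, a 30% saving and a twofold gap, from −8.0 to −7.6 minutes. A reader might also infer that the estimate is noisier, as if fewer charts had been read. It is not: the actual SE is unchanged, and only the reported SE is inflated.

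It is also fair that complementary allocation is inferred from the paired design and not stated, and that an adjusted log-scale analysis changes the effect measure from minutes to a ratio. The fix should say so.

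**Conclusion.** The point holds as one of test naming and of a mismatch between design and analysis. It is minor to moderate in weight and sits on a secondary aim. Signed-rank is the probable intent. It leaves the coordinators' speed gap in the differences, which makes the test conservative and the interval too wide: by about 12% to 32% at an assumed 1.5-fold gap, with a power loss of about 9 to 17 percentage points at an 8% saving (48 − 39 and 89 − 72, two-sided). At a gap of about 1.2 times the loss is a few points; at a 15% saving it is nearly nil. A positive result would still stand. In the post-hoc strata coordinator balance is only approximate, but the unadjusted test remains valid.

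The direction of the effect follows from the allocation, given one review of each kind per chart. The sizes are illustrative, because the documents give no timing SD, correlation, speed gap or expected saving.

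**What to change.** In Section 9, name the Wilcoxon signed-rank test as the paired test and account for coordinator in the efficiency comparison and its interval. Either of two methods would do:

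- For each chart, take the log ratio of coordinator 1 to coordinator 2 minutes and compare it between the two allocation groups by a Wilcoxon test. Half the Hodges-Lehmann shift, exponentiated, is the Human+AI to Human-alone time ratio, reported with its 95% interval.
- Fit a mixed model to log minutes, with arm and coordinator fixed and chart random.

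Say which result decides the speed hypothesis; I would use the adjusted one. State that it reports a time ratio, averaged over the two coordinators, and keep median minutes per arm as the descriptive summary. Use the same method in the stratified efficiency analyses. In Section 5.1, state that the coordinators' halves are complementary, so that each chart gets one manual and one AI-assisted review by different people.

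The cost is some wording, slightly more analysis work and an effect measure on the ratio scale. No new reviews or data are needed, and if the coordinators are equally fast no power is lost (88.9% signed-rank, 89.0% adjusted).

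### The 12 criterion-level tests use single-step Bonferroni, which is valid; Holm's step-down would keep the same 5% familywise error and recover some power (optional improvement)

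*Combined protocol and SAP*

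**What the plan says.** Section 9 (Analysis plan) sets out the criterion-level comparison after the main analyses.

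- **Status:** "The following are post-hoc analyses to be conducted after the pre-specified main analyses". The criterion-level comparison is one of these.
- **Test:** "To assess criterion-level accuracy, a two-sided, paired t-test will be conducted", once per criterion.
- **Multiplicity:** the test "will be conducted with Bonferroni correction for multiple hypotheses", with alpha = 0.05/n, "where $n=12$ was the number of criteria studied". No stepwise procedure is mentioned.
- **Follow-up:** a further one-sided test of Human+AI superiority is planned "For any criterion with a statistically significant difference in mean criterion-level accuracy". Its significance level is not stated separately. The general statement is that analyses "will rely on a predetermined significance level", with 0.05 as the example.
- **Power:** none is claimed for these tests. The statement that "400 individual patients will achieve an estimated statistical power greater than 90% for this non-inferiority study" concerns the chart-level comparison only.
- **Reporting:** descriptive summaries are planned for each analysis, with effect sizes and confidence intervals where applicable.

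**The concern.** Single-step Bonferroni holds every criterion to 0.0042 however strong the evidence on the other 11. Holm's procedure relaxes the threshold each time a hypothesis is rejected and needs no further assumption. This suits criteria abstracted from the same chart by the same reviewer, where correlation is plausible.

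The first-step test is also a gate. A criterion that misses the threshold loses its significance label and does not go on to the one-sided superiority test. Because the first step is two-sided, a loss of accuracy with AI can miss the label just as a gain can. At stake is how many truly different criteria are identified in a supporting analysis.

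**Working it through.** **1. The plan's own figure.** 0.05/12 = 0.004167. The Bonferroni bound is 12 × 0.004167 = 0.05. If the 12 tests were independent, the familywise error would be 1 - (1 - 0.004167)^12 = 0.0489, against 1 - 0.95^12 = 0.460 with no correction. The stated level reproduces and the correction does its job.

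**2. Holm thresholds.** Order the p-values from smallest to largest. Compare the i-th with 0.05/(13 - i) and stop at the first failure: 0.00417, 0.00455, 0.00500, 0.00556, 0.00625, 0.00714, 0.00833, 0.01000, 0.01250, 0.01667, 0.02500, 0.05000. The first threshold equals Bonferroni's and the rest are larger. So Holm keeps every Bonferroni rejection and may add others, but it does not make the first rejection easier.

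**3. Inputs for the size of the gain.** From Section 9: 12 two-sided tests, familywise 5%, 400 charts. Not in the documents, and therefore assumed: the true difference d, the proportion of discordant charts, the correlation between tests, the number k of criteria that truly differ, and that all 400 charts contribute to every criterion. Each criterion is treated as correct or incorrect per chart, so the paired difference has variance (discordance - d²).

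**4. Bonferroni power per criterion.** SE = √[(discordance - d²)/n]; power ≈ Φ(d/SE - 2.865), where 2.865 is the two-sided critical value at 0.05/12.

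- d = 0.08, discordance 0.20, n = 400: SE = √[(0.20 - 0.0064)/400] = 0.0220; d/SE = 3.636; power = Φ(0.771) = 78%.
- d = 0.05, discordance 0.20, n = 400: SE = √[(0.20 - 0.0025)/400] = 0.0222; d/SE = 2.250; power = Φ(-0.615) = 27%.

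**5. Holm against Bonferroni by simulation.** Sets of 12 z-tests were simulated, 100,000 per row. Power is the average over truly different criteria. The last column is the share of studies in which Holm flags at least one more criterion.

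| Scenario (n = 400, 20% discordance) | k | Bonferroni | Holm | Extra flag |
|---|---|---|---|---|
| 8 points, independent | 3 | 78% | 79% | 5% |
| | 6 | 78% | 82% | 22% |
| | 9 | 78% | 85% | 50% |
| | 12 | 78% | 92% | 82% |
| 8 points, correlation 0.5 | 3 | 78% | 79% | 4% |
| | 6 | 78% | 81% | 18% |
| | 9 | 78% | 84% | 39% |
| 5 points, independent | 3 | 27% | 27.5% | 2% |
| | 6 | 27% | 28.4% | 8% |
| | 9 | 27% | 29.4% | 19% |

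Other cases, independent tests:

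- 3-point differences, 3 to 9 criteria: gain at most 0.2 points, extra flags in under 2% of studies.
- 8 points with 10% discordance: Bonferroni power is already 99%, so the gain is under 1 point.
- One true difference: gain about zero in every scenario.
- 200 charts (an assumption, for criteria assessable in one tumor type only), 8 points, 20% discordance: 38% with Bonferroni; 39%, 41% and 43% with Holm for k = 3, 6 and 9.

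Holm's simulated familywise error stayed within 5% throughout, and no Bonferroni rejection was lost.

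**The case against.** The strongest reply is that nothing here is wrong. The plan names its method, gives the divisor and controls the familywise error. The tests are labelled post hoc, no power is promised for them, and strictness is a defensible choice for such tests. All of this stands.

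The size of the gain also rests on figures that the documents do not supply. An 8-point difference is larger than the plan's own chart-level margin ("Non-inferiority margin, set as 0.05 for conservative sample size estimates"), and 9 such differences out of 12 is near the favorable end. A uniform 400 charts is not established either: Section 8.2 lists separate biomarkers for colorectal cancer and NSCLC, and the 12 criteria are not mapped to those elements. These objections stand, and they are why the gain is given as a range that starts at zero.

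Holm has a cost too. Bonferroni gives matching simultaneous confidence intervals at level 1 - 0.05/12, whereas Holm has no equally simple counterpart, and Section 9 promises intervals where applicable. A borderline criterion could be significant under Holm while its Bonferroni-level interval includes zero. So it would be wrong to infer that the change has no downside.

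A reader might also infer that Bonferroni leaves real differences unreported. The documents do not support that: Section 9 plans descriptive summaries, effect sizes and intervals, so estimates can be shown for every criterion. Only the significance label and entry to the follow-up test depend on the threshold.

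What survives all of this is that Holm rejects at least as much as Bonferroni at the same familywise error, under any dependence.

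**Conclusion.** The point holds as an optional efficiency gain. It would be too strong to read it as an error in the plan, because the Bonferroni rule is valid and its level is correctly computed.

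For 400 charts, 20% discordance and independent tests, the gain in power per truly different criterion is:

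- about 0 points if only one criterion differs or if effects are small;
- 0.5 to 2.5 points for 5-point differences in 3 to 9 criteria;
- 1 to 7 points for 8-point differences in 3 to 9 criteria;
- about 14 points if all 12 criteria differ by 8 points.

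The direction of the gain is guaranteed; its size depends on these assumptions. The chart-level non-inferiority test, the efficiency analysis and the sample size do not change.

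**What to change.** In Section 9, replace the fixed 0.05/12 rule with Holm's step-down procedure over the 12 criteria at a familywise 5%, and report Holm-adjusted p-values. For the i-th smallest p-value, the adjusted value is the largest of (13 - j) × p(j) over j ≤ i, capped at 1. Use these to decide which criteria enter the one-sided superiority test.

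State that confidence intervals for the criterion-level differences are reported at the 1 - 0.05/12 level (99.58%), and that a borderline criterion may be significant under Holm while its interval includes zero.

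The cost is a change of phrase, one added sentence, and a calculation simple enough to do by hand or in the R or STATA already planned. No extra charts or data are needed.
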